#### 3 TRIAL DESIGN

This is a non-randomised, open, single arm, two-stage, multi-centre phase II trial evaluating efficacy of cemiplimab (continue until progression) in patients with IaBCC.

The trial aims to recruit 41 patients with laBCC, who will receive the following regimen:

cemiplimab 350mg on day 1 only of each 21 day cycle, over a maximum period of 2 years.

Assessment of response will be done after cycle 4 and then every 12 weeks whilst on trial and progression free.

The planned recruitment duration for this study is 2 years. Patients will have up to 24 months of treatment and will be followed for a further 24 months after treatment ends at 3, 6, 9, 12, 18 and 24 months.

#### 4 PATIENT SELECTION AND ELIGIBILITY

#### 4.1 Source of patients

Locally advanced basal cell carcinoma is a rare disease and there is a requirement that all patients are managed under the auspices of a super-specialist (SS-MDT) multidisciplinary team.

Patients with IaBCC will be eligible if they have measurable disease (either a bidimensional visible lesion that is ≥10 mm in both the longest diameter and the perpendicular diameter to be followed by digital medical photography or a target lesion according to RECIST 1.1 that can be followed radiologically) and are fit to receive immunotherapy. Discussion within the SS-MDT of all eligible patients is encouraged.

Patients participating in the IMPACT Trial will not be denied access to any standard of care therapy,

#### 4.2 Number of patients

41 patients will be recruited across multiple sites, aiming to recruit 37 evaluable patients.

#### 4.3 Inclusion Criteria

- 1. Signed informed consent
- 2. Men and women age ≥ 18 years
- ECOG performance status 0 or 1
- 4. Histologically confirmed disease (from diagnostic biopsy) that is considered to be inappropriate for surgery (see below), in the opinion of a Super Specialist-MDT (SS-MDT) reason must be fully documented:

Acceptable inoperable / medical contraindications to surgery include:

- a. BCC that has recurred in the same location after two or more surgical procedures and curative resection is deemed unlikely
- b. BCC ≥10 mm, and relapsing after 2 surgeries in critical locations (e.g. periocular and perioral areas)
- c. BCC infiltrating in bone/cartilage/other structures or with significant local invasion and curative resection is unlikely

- d. Relapsing BCC after multiple surgeries and/or radiotherapy
- e. BCC in patients whose co-morbidities preclude them from general anaesthesia/surgery.
- f. BCC in anatomically challenging locations/size for which surgery may result in substantial morbidity and/or deformity (e.g. removal of all or part of a facial structure, such as nose, ear, eyelid, eye; or requirement for limb amputation); or patient's reluctance to accept the consequences of surgery.
- 5. Patients must be deemed as inappropriate for radiotherapy in the opinion of a SS-MDT. Specifically, patients must meet at least 1 of the following criteria (reason must be fully documented):
  - a. A patient previously received radiotherapy for BCC, such that further radiotherapy would exceed the threshold of acceptable cumulative dose, as per the clinical oncologist.
  - b. Judgment of clinical oncologist that such tumour is unlikely to be curative or radiotherapy was deemed to be contraindicated.

Acceptable contraindications to radiotherapy for patients who have not received any prior radiation include:

- a. laBCCs in anatomically challenging locations for which radiotherapy would be associated with unacceptable toxicity risk in the context of the patient's overall medical condition in the opinion of the multidisciplinary team.
- b. Radiotherapy is contraindicated or inappropriate (limitations because of location of tumour, or cumulative prior radiotherapy dose).
- 6. There must be at least 1 measureable baseline lesion. For visible lesions the longest diameter (LD) and the perpendicular diameter must both be ≥10 mm if followed by digital medical photography. Non-measurable disease for laBCC is defined as either uni-dimensionally measurable lesions, tumours with margins that are not clearly defined, or lesions with maximum perpendicular diameters less than 10 mm. Patients without measureable disease at baseline are not eligible for the study In patients with a deeply invasive lesion that the investigator deems is best measured by magnetic resonance imaging (MRI) or computed tomography (CT), measurement for that target lesion will be done according to RECIST 1.1 criteria. The requirement for a lesion to be measurable by RECIST 1.1 is that it must be ≥10 mm in longest dimension.

If a previously radiated lesion is to be followed as a target lesion, progression must be confirmed by biopsy after radiotherapy. Previously irradiated lesions may be followed as non-target lesions if there is at least 1 other measurable target lesion

- 7. Hepatic function:
  - a. Total bilirubin ≤1.5x upper limit of normal (ULN).
  - b. Patients with Gilbert's Disease and total bilirubin up to 3x ULN are eligible
  - c. Transaminases ≤3x ULN
  - d. Alkaline phosphatase (ALP) ≤2.5x ULN
- 8. Renal function: estimated creatinine clearance
  - >30 mL/min (calculated using the CKD-EPI formula see Appendix 3)
- 9. Bone marrow function:
  - a. Haemoglobin ≥9.0 g/dL
  - b. Absolute neutrophil count (ANC) ≥1.5 x 10^9/L
  - c. Platelet count ≥75 x 109/L

#### 4.4 Exclusion Criteria

- 1. ECOG Performance Status ≥ 2
- 2. Patients with metastatic BCC or Gorlins syndrome are excluded.
- 3. History of severe hypersensitivity reaction (≥grade 3) to polysorbate 80 containing drugs
- 4. Immunosuppressive corticosteroid doses (>10 mg prednisone daily or equivalent) within 4 weeks prior to the first dose of cemiplimab
  - Note in clarification: Patients who require brief courses of steroids (e.g. as prophylaxis for imaging studies due to hypersensitivity to contrast agents) are not excluded
- 5. Active infection requiring therapy, including positive tests for human immunodeficiency virus (HIV)-1 or HIV-2 serum antibody, hepatitis B virus (HBV), or hepatitis C virus (HCV). Patients with controlled HIV (undetectable viral load and CD4 count above 350) can be included in the study
- 6. History of pneumonitis within the last 5 years
- 7. Treatment with systemic immunostimulatory agents (including, but not limited to, IFNs, IL-2) within 28 days or 5 half-lives of the drug, whichever is shorter, prior to treatment start (Cycle 1 Day 1)
- 8. Treatment with PI3K inhibitors e.g. idelalisib
- 9. Ongoing or recent (within 5 years) evidence of significant autoimmune disease that required treatment with systemic immunosuppressive treatments, which may suggest risk for immune-related adverse events (irAEs). The following are not exclusionary: vitiligo, childhood asthma that has resolved, type 1 diabetes, residual hypothyroidism requiring only hormone replacement, or psoriasis that does not require systemic treatment.
- 10. Any anticancer treatment within 30 days of the initial administration of cemiplimab or planned to occur during the study period other than palliative radiotherapy (chemotherapy, targeted systemic therapy, imiquimod, photodynamic therapy), either investigational or standard of care.
- 11. Breastfeeding
- 12. Positive serum pregnancy test (a false positive pregnancy test, if demonstrated by serial measurements and negative ultrasound, will not be exclusionary)
- 13. Women of childbearing potential (WOCBP fertile following menarche and until becoming post-menopausal unless permanently sterile) or sexually active men, who are unwilling to practice highly effective contraception prior to the initial dose/start of the first treatment, during the study, and for at least 6 months after the last dose. Contraception is not required for men with documented vasectomy. Postmenopausal women must be amenorrheic for at least 12 months in order not to be considered of childbearing potential. Pregnancy testing and contraception are not required for women with documented hysterectomy, bilateral salpingectomy or bilateral oophorectomy.
- 14. Receipt of live vaccines (including attenuated) within 30 days of first study treatment

- 15. Any acute or chronic psychiatric problems that, in the opinion of the investigator, make the patient ineligible for participation.
- 16. History of an additional malignancy within 5 years of registration with the exception of those malignancies with a negligible risk of metastasis or death and treated with curative intent. Patients with CLL who have not required systemic treatment within 6 months of enrolment are not excluded.
- 17. Other concurrent serious illness or medical condition that in the investigator's opinion precludes entry into the trial.
- 18. Prior treatment with an agent that blocks the PD-1/PD-L1 pathway.
- 19. Prior treatment with other systemic immune-modulating agents within fewer than 28 days prior to the first dose of cemiplimab. Examples of immune-modulating agents include therapeutic vaccines, cytokine treatments, or agents that target cytotoxic T-lymphocyte antigen 4 (CTLA-4), 4-1BB (CD137), or OX-40.
  - Note in clarification: Prior treatment with imiquimod or other topical or intralesional immune modulators will not be exclusionary

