#### 5 REGISTRATION

It is the responsibility of the Principal Investigator (PI), or a person delegated by the PI (as documented on the delegation log) to obtain written informed consent from each subject **prior** to participation in this study, following adequate explanation of the aims, methods, study procedures and any risks. Please refer to Appendix 6 for contingency measures during extenuating circumstances.

After each patient has given written informed consent and completed the necessary study specific procedures as set out under baseline procedures (section 6.1) and in the visit schedule (section 6.6), an eligibility checklist must be completed prior to registration. The following information will be required:

- Confirmation that the patient is eligible for the trial by completion of the checklist;
- Confirmation that the measurable disease being followed in the trial has been assessed by photography and/or MRI/ CT scan within 6 weeks of scheduled start date of treatment;
- Confirmation that the patient has given written informed consent;

Central registration will be performed by the investigator-led study (ILS) team part of the Clinical Trials Unit (Bristol Haematology and Oncology Centre), on behalf of the sponsor (UHBW). The checklist will be sent to the ILS team who will confirm eligibility and register the patient onto the trial. The patient will be assigned a unique trial identification number (Trial ID). This Trial ID is recorded on all documentation and will be used for identification purposes in the IMPACT study only.

To register a patient, please send the eligibility checklist by email to:

[contact] (08.30 – 17.00 Monday to Friday)

Patients should commence trial treatment within 3 weeks of registration.

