#### 6 STUDY PROCEDURES AND EVALUATIONS

#### 6.1 **Baseline** (within 7 days of registration)

Patients will undergo general assessment and assessment of their disease to include:

- Physical examination to assess fitness (including height and weight); ECOG performance status; vital signs (blood pressure, heart rate, oxygen saturation, temperature).
- Recording of concomitant medication use, with relevant dates.
- Medial and cancer history.
- ECG.
- Photography of skin lesion(s), including those to be followed as target lesions within 6 weeks of scheduled start date of immunotherapy. Target lesions need to be ≥10mm in both the longest diameter and the perpendicular diameter.
- MRI/ CT scan (with IV contrast) of the area encompassing the primary tumour (e.g. head and neck, chest, abdomen etc) to be performed within 6 weeks of scheduled start date of immunotherapy. If the lesions are in the head and neck region an MRI scan would be preferred. This scan will document any deeper extent of disease and whether this modality will be used to follow any target lesion(s). The same modality used to document target lesion extent at baseline must be used throughout the study.
- Full blood count, U+Es (including urea, sodium, potassium, total calcium and creatinine), liver function tests (to include ALP, ALT, Albumin and Bilirubin), LDH, thyroid function tests (including TSH, T4 and if required T3), cortisol and glucose (random). NB cortisol levels need to be measured ideally before 9am.
- Viral screen to include HIV, Hepatitis B and Hepatitis C. Patients with well controlled HIV will need to show undetectable viral load and CD4 counts over 350 to confirm inclusion into the study.
- Serum pregnancy test if required
- Estimated GFR to be assessed according to local practice (recommended technique of eGFR using the CKD-EPI formula (see Appendix 3)).
- Baseline assessment of symptoms using common toxicity scoring (CTCAE v5.0).
- Completion of Quality of life questionnaires EQ-5D-5L, EORTC QLQ-C30, Skindex-16, FNAE and the Hornheide questionnaire.

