# 6.5 Procedures for assessing efficacy

6.5.1 Photography of skin lesions and MRI/CT scan of the area encompassing the primary tumour

The primary endpoint ORR will be assessed for externally visible tumour(s) which are

being used as target lesions using **clinical response criteria** (Appendix 2 table 1) according to World Health Organisation (WHO) criteria. This requires photography that shows bi-dimensional measurements (≥10mm in longitudinal dimension and ≥10mm in the perpendicular dimension). If patients only have target lesions being assessed radiologically using MRI/CT scan (target lesion ≥10mm in the longest diameter) ORR will be assessed using **RECIST 1.1 criteria**. Patients who have target lesions measurable by both clinical response criteria and radiologically by RECIST 1.1 will have their outcome assessed using **composite response criteria** (Appendix 2 table 2).

Please see Appendix 1 and Appendix 2 for more information.

The MRI/CT scan and photography must be completed at baseline (within 6 weeks of the first dose of trial treatment) in order to identify the target lesions. Photographs and scans must be sent to the study team for central review within 5 days of assessment. Please refer to the imaging manual for more information.

Objective tumour response to treatment will be assessed after cycle 4 (12 weeks +/-7 days from cycle 1 day 1) and before cycle 5, and then every 12 weeks (+/- 7 days from the previous photography/scan) whilst the patient is on treatment. If the patient stops treatment for any reason other than disease progression target lesions will continue to be assessed every 12 weeks (+/- 7 days) until disease progression for a maximum of 12 months. Photographs and scans must be sent to the study team for central review within 5 days of assessment. Please refer to the imaging manual for more information.

Please refer to Appendix 6 for contingency measures during extenuating circumstances.

Complete response can only be confirmed with clinical biopsy otherwise response remains as partial response.

Baseline	Scan 1	Subsequent scans	End pf treatment and in				
		on treatment	follow up				
Within 6 weeks of Cycle1 Day1	12 weeks (+/- 7 days) from Cycle1 Day1 but before Cycle 5	Every 12 weeks (+/- 7 days) from previous photography/scan	If no progression, photography and MRI/CT scans should continue every 12 weeks (+/- 7 days) from previous				
			photography/scan				

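### Exclusion criteria 10 and 19 are not reconciled on imiquimod, and the baseline measurement may precede the last prior treatment, so shrinkage from another treatment can enter the ORR

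*Protocol*

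**What the plan says.** **Prior treatment (Protocol section 4.4).** Criterion 10 excludes "Any anticancer treatment within 30 days of the initial administration of cemiplimab or planned to occur during the study period". The criterion then states its one exception, followed by a list in brackets: "other than palliative radiotherapy (chemotherapy, targeted systemic therapy, imiquimod, photodynamic therapy), either investigational or standard of care". The bracketed list stands directly after the radiotherapy exception, but none of its items is radiotherapy, so it can only be read as examples of what is barred. Imiquimod is one of them.

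Criterion 19 excludes "Prior treatment with other systemic immune-modulating agents within fewer than 28 days prior to the first dose of cemiplimab". Its clarifying note adds: "Prior treatment with imiquimod or other topical or intralesional immune modulators will not be exclusionary". The note gives no interval and does not refer back to criterion 10.

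**Baseline measurement.** Section 5 asks the site to confirm that the measurable disease "has been assessed by photography and/or MRI/ CT scan within 6 weeks of scheduled start date of treatment". Section 6.1 lists "Photography of skin lesion(s), including those to be followed as target lesions within 6 weeks of scheduled start date of immunotherapy" and sets the same limit for MRI/CT. Section 6.5.1 says these images "must be completed at baseline (within 6 weeks of the first dose of trial treatment) in order to identify the target lesions". The visit schedule (section 6.6, note 6) and Appendix 1 repeat the six-week limit. None of these places mentions the date of the last prior treatment.

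**Safeguards for treated lesions.** Inclusion criterion 6 requires biopsy-confirmed progression before an irradiated lesion can be a target. Appendix 1 treats a lesion in an area given other loco-regional therapy as non-measurable until it has been shown to progress. The same appendix sends the reader to Appendix 2 for measuring skin lesions, and Appendix 2 has no equivalent rule.

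**The concern.** The primary endpoint is the proportion of patients whose tumour has shrunk enough from its baseline size by 6 months. In a single-arm trial that baseline is the only comparator. If another active treatment is given after the reference photograph or scan, whatever it achieves is measured as if cemiplimab had done it, and no control group would show this.

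Nothing later corrects the reference. Appendix 2 expects baseline measurements to be completed, in general, on the day of photography, and the next scheduled images come 12 weeks after cycle 1 day 1. The four-week maintenance rule for a visible response does not help, because the same too-large baseline remains the reference.

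The situation is foreseeable. Section 1 counts topical treatment and photodynamic therapy (PDT) among the common treatments for BCC, and criterion 10 restricts earlier targeted systemic therapy only by timing.

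The imiquimod wording adds a second problem. Sites working from an eligibility checklist can reach different answers for the same patient, so both the population and the exposure to carry-over can vary by site.

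**Working it through.** **1. Imiquimod.** Take a patient who last used imiquimod 14 days before first dose.
- Criterion 10: 14 is less than 30, so excluded.
- Note to criterion 19: prior imiquimod does not exclude, at any interval.

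If the note governs criterion 19 only, the patient is excluded. If it is read as a general clearance, the patient is eligible. The text does not say which reading is meant.

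**2. Windows.**
- Oldest permitted baseline image: 6 × 7 = 42 days before first dose.
- Period in which prior treatment is barred: 30 days before first dose.
- Difference: 42 − 30 = 12 days.

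Example: image on day −42, targeted systemic therapy until day −31, cemiplimab on day 0. The image is within 42 days and the last treatment is more than 30 days back. The two timing rules are met, and the reference size predates treatment that continued after it. For topical or intralesional agents the exposed interval could be the whole 42 days if the note is read as a general clearance.

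**3. The plan's own design (section 11.1).** Inputs: 18 patients at stage 1, continue at 6 or more responses, 19 more at stage 2 (total 37), 25% against 45%, alpha 5%, power 80%. The protocol gives no final cut-off, so I searched for it with

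P(positive | p) = Σ over x = 6 to 18 of Bin(x; 18, p) × P(Y ≥ c − x), Y ~ Bin(19, p).

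| Cut-off c of 37 | p = 0.25 | p = 0.45 |
|---|---|---|
| 13 or more | 0.0876 | 0.8523 |
| 14 or more | 0.0496 | 0.8060 |
| 15 or more | 0.0249 | 0.7320 |

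Only 14 or more meets both targets, so the design reproduces with that cut-off. Counting 15 or more of 18 as an early success changes neither figure to four decimals.

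**4. Weight of one false responder.** 1/37 = 2.7 percentage points of the final ORR; 1/18 = 5.6 points at stage 1.

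**5. Illustration only.** The protocol gives no carry-over rate. Assume that a share f of true non-responders is counted as responders, that the true ORR is 25% and that the cut-off is 14 of 37. The apparent rate is then 0.25 + 0.75f, and the expected number of false responders is 37 × 0.75 × f.

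| f | False responders expected | Apparent rate | Pass stage 1 | Positive trial |
|---|---|---|---|---|
| 0 | 0 | 0.250 | 0.28 | 0.050 |
| 2% | 0.6 | 0.265 | 0.34 | 0.076 |
| 5% | 1.4 | 0.2875 | 0.42 | 0.130 |
| 10% | 2.8 | 0.325 | 0.56 | 0.264 |

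If 2% or 5% is instead taken as a share of all patients, the apparent rate is 0.27 or 0.30 and the chance of a positive trial is 0.086 or 0.169. One certain false responder in stage 1 gives 0.084; one in each stage gives 0.125.

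**The case against.** **Exclusion criteria are cumulative.** Meeting any one excludes, and a note under one criterion does not waive another. Criterion 19 concerns systemic agents, so its note may say only that topical and intralesional agents fall outside that criterion. On this reading imiquimod is allowed, but not within 30 days. This is a fair reading and may be the intended one. It does not settle the matter: criterion 19 is already limited to systemic agents, so a note on topical agents is easily taken as a general clearance, and there is no cross-reference to prevent that.

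**Criteria 7 and 19.** A reader might infer a second contradiction, because criterion 7 uses "within 28 days or 5 half-lives of the drug, whichever is shorter" and criterion 19 a flat 28 days. The text does not support it. Both apply, so for agents covered by both, the flat period decides and the shorter option in criterion 7 has no effect. That is redundancy.

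**The section 6.1 heading.** It places baseline within 7 days of registration, and section 5 says treatment should start within 3 weeks of registration. Together that is 7 + 21 = 28 days, inside the washout. But photography and MRI/CT carry their own six-week window, repeated in four other places, and that specific window is the one sites will apply.

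**Existing safeguards.** A reader might infer that lesions treated topically or by PDT have no protection. That goes too far: the Appendix 1 rule on prior loco-regional therapy plausibly reaches them, at least for target lesions measured by RECIST. Appendix 1 also wants baseline evaluation as near to treatment start as possible. Criterion 10 bars treatment planned during the study period, although it does not say when that period begins. These narrow the route. They do not clearly cover photographed skin lesions, do not reach systemic therapy, and do not order the baseline image against the last treatment.

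**Rarity.** A site would have to image a lesion for the trial, continue other treatment and stop by day −31. Section 1 reports that vismodegib is not recommended by NICE and that sonidegib has not been appraised, so recent targeted therapy should be uncommon. A visible partial response needs a 50% fall in the sum of products. This stands: few patients are likely to be affected.

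**Conclusion.** Two defects stand. Criterion 10 and the note to criterion 19 give different answers on recent imiquimod unless the reader supplies a limit that the note does not state. And the permitted windows allow the reference measurement for the primary endpoint to predate another active treatment: by up to 12 days under criterion 10, longer for topical agents if the note is read broadly.

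The size of the resulting bias cannot be derived from the protocol. What is certain is the weight of each false responder: 2.7 points on 37 patients and 5.6 points on 18. A reader might infer from the illustration that the false-positive rate is 13% or 17% in place of 5%. The protocol does not support that. Those figures rest on an assumed carry-over rate and a derived cut-off, and show only that a design this small is sensitive to one or two misattributed responses.

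The correction is worth making because it is specific and cheap, and because a single-arm trial cannot detect the problem afterwards.

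**What to change.** 1. **Section 4.4.** Reconcile criterion 10 with the note to criterion 19 and cross-refer them. Which rule applies to recent topical or intralesional treatment is for the sponsor and investigators to decide; the text needs to give one answer.
2. **Sections 5 and 6.1 and the eligibility checklist.** Require that the baseline photography and MRI/CT used as the response reference be taken after the last prior anticancer treatment, whether systemic, topical, intralesional or PDT, and repeated before cycle 1 if they were not. Record both dates on the checklist.
3. **Appendix 2.** State whether the Appendix 1 rule on lesions in areas given other loco-regional therapy applies to photographed skin lesions.

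The cost is a wording amendment and a checklist line, with baseline imaging timed later, or occasionally repeated, for a few patients. The sample size and decision rules do not change. The ordering rule removes treatment given after the reference image; a late effect of treatment finished before the image would remain possible.

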#### **TRIAL SCHEMA**

#### TRIAL SUMMARY

Title

Efficacy and safety of first line Cemiplimab in advanced BCC: A phase 2 trial (IMPACT)

Objective

To evaluate the benefit and safety of cemiplimab, a fully human anti-PD-1 monoclonal antibody in patients with locally advanced BCC

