In the UK, NICE has appraised that vismodegib is not recommended within its marketing authorisation for treating symptomatic mBCC, or laBCC that is inappropriate for surgery or radiotherapy, in adults because of the uncertainty in the evidence and because it is not cost effective (https://www.nice.org.uk/guidance/ta489/chapter/1-Recommendations). To date sonidegib has not been appraised by NICE. Hence, there is no valid, effective first-line treatment option for patients with laBCC or mBCC in the UK. Recently there has been a case series of 2 cases treated with nivolumab and pembrolizumab as first-line therapy in laBCC showing impressive responses (19). The potential advantages to using anti-PD-1 over hedgehog pathway inhibitors include improved medication compliance (intravenous route of administration) and the potential for long-term durable responses including complete responses. This suggests that anti-PD-1 therapy may be a feasible frontline therapeutic option in patients with advanced BCC.

Hence, we propose to evaluate the safety and efficacy of first line cemiplimab in patients with advanced BCC in this phase II trial.

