# 11.1 Sample size calculations

The hedgehog pathway inhibitors (HHIs) have shown an ORR of about 45% in the first line setting. In the ERIVANCE study, the ORR with vismodegib was 42.9% at 9 months follow-up which increased to 47.6% at 21 months follow-up (9). In the BOLT study of sonidegib, the ORR was 47.0% at primary 6 month follow-up, increasing to 56.1% (95% CI: 43.3–68.3) at 18 month follow-up (10). In the second line setting, cemiplimab showed an ORR of 31%, in a recently reported phase 2 study in the 2nd line setting (18), after a median follow-up of 15 months.

Assuming an ORR of cemiplimab to be around 45% at 6-months in the first line setting, this study is powered as a single arm Simon II Stage design. This will be used to differentiate between a poor treatment (success rate of 25%) and a good treatment (success rate 45%) using a nominal significance level alpha = 5% and a power of 80%.

Once 18 patients are recruited, an interim analysis will be performed with the decision rule of progression to Stage II if 6 or more of the 18 patients achieve a response. If ≤5 patients have responded (poor response) or if 15 out of the 18 patients have responded (exceptional response) the trial will be stopped.

Stage II will be the recruitment of a further 19 patients. To account for a potential loss of non-evaluable patients (assuming a 10% drop out rate) the sample size will be inflated to N = 41.

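### The trial is labelled and sized as first line, but sections 4.3 and 4.4 admit patients who stopped a hedgehog inhibitor more than 30 days before cemiplimab

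*Protocol*

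**What the plan says.** **Population named.** The Trial Summary gives the title as "Efficacy and safety of first line Cemiplimab in advanced BCC: A phase 2 trial (IMPACT"). Section 1 closes with the aim: "we propose to evaluate the safety and efficacy of first line cemiplimab in patients with advanced BCC in this phase II trial". Section 11.1 ties the 45% target at 6 months to first-line use and supports it with first-line hedgehog-inhibitor results.

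**What second line means here.** Section 1 says cemiplimab is already licensed as second-line treatment for patients whose disease advanced on a hedgehog inhibitor or who could not tolerate one. Section 11.1 reports: "In the second line setting, cemiplimab showed an ORR of 31" per cent, after a median follow-up of 15 months.

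**Who may enter.** Neither section 4.3 nor the summary criteria say anything about earlier systemic treatment. In section 4.4:
- Criterion 18 excludes, with no time limit, "Prior treatment with an agent that blocks the PD-1/PD-L1 pathway". Criterion 8 does the same for PI3K inhibitors.
- Criterion 10 excludes "Any anticancer treatment within 30 days of the initial administration of cemiplimab or planned to occur during the study period other than palliative radiotherapy". Its examples are "chemotherapy, targeted systemic therapy, imiquimod, photodynamic therapy), either investigational or standard of care". Hedgehog inhibitors fall under targeted systemic therapy, so they are barred only within that window.
- Criteria 7 and 19 set short washouts for immune-stimulating and immune-modulating agents.

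No item names hedgehog inhibitors or requires patients to be untreated systemically.

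**The concern.** A washout implies that earlier use is acceptable. A patient who progressed on vismodegib or sonidegib and stopped 31 days before the first cemiplimab dose passes every listed criterion. That is the kind of patient the Background places in the already licensed second-line setting. Registration under section 5 runs on an eligibility checklist, and a restriction found only in the title is not a listed criterion.

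Two things are at stake. The first is interpretation. A response rate from mixed lines of treatment cannot be presented plainly as first-line, or set beside the first-line hedgehog-inhibitor rates in section 11.1. A disappointing result could be put down to dilution, and a good one challenged as not first line. The second is power. The design has little slack above 80%, so patients expected to respond less often reduce it.

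This is not a detail that can wait for an analysis plan, because an analysis plan cannot change who was enrolled.

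**Working it through.** **Inputs, all from section 11.1 unless noted**
- Poor rate 25%, good rate 45%, alpha 5% (taken as one-sided, as is usual for a Simon design), power 80%.
- Stage I: 18 patients, continue with 6 or more responders. Stage II: 19 more, total 37.
- Second-line cemiplimab response rate: 31%.
- Final cut-off: not stated, so inferred below.
- Share *f* of patients with an earlier hedgehog inhibitor: not given anywhere, so an assumption shown as a range.

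**Step 1. Reproduce the design.** For a true response rate *p* and final cut-off *c*,

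P(success) = Σ over x = 6,…,18 of Bin(x; 18, p) × P(Y ≥ c − x), with Y ~ Bin(19, p).

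| Cut-off of 37 | Alpha (p = 25%) | Power (p = 45%) |
|---|---|---|
| ≥13 | 0.0876 | 0.852 |
| ≥14 | 0.0496 | 0.806 |
| ≥15 | 0.0249 | 0.732 |

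Only 14 or more meets both stated limits. The plan's 37 is therefore reproduced, with alpha 4.96% and power 80.6%. The upper stop at 15 of 18 does not change these figures.

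**Step 2. Mix the populations.** The expected response rate is p = 0.45(1 − f) + 0.31f = 0.45 − 0.14f. Put this *p* into the Step 1 formula with cut-off 14. The chance of stopping for poor response at stage I is P(Bin(18, p) ≤ 5).

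| Pre-treated share *f* | Expected ORR | Power | Stage I poor-response stop |
|---|---|---|---|
| 0 | 45.0% | 80.6% | 10.8% |
| 1 of 37 (2.7%) | 44.6% | 79.4% | 11.4% |
| 2 of 37 (5.4%) | 44.2% | 78.2% | 12.0% |
| 10% | 43.6% | 75.9% | 13.1% |
| 20% | 42.2% | 70.7% | 15.9% |
| 30% | 40.8% | 64.8% | 18.9% |

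Worked example for 20%: 0.45 − 0.14 × 0.20 = 0.422. In patients, 10% of 37 is 3.7, 20% is 7.4 and 30% is 11.1.

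The loss is 80.6 − 79.4 = 1.2 points for one pre-treated patient, 80.6 − 78.2 = 2.4 for two, and 80.6 − 70.7 = 9.9 at a 20% share.

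**Step 3. Check the timing of the two rates.** The 31% follows a median of 15 months, whereas the 45% is a 6-month assumption. The hedgehog-inhibitor rates in section 11.1 rise with follow-up (42.9% to 47.6%, and 47.0% to 56.1%). If cemiplimab behaves likewise, its second-line rate at 6 months would be no higher than 31%. That is a conditional argument, not a measurement.

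**The case against.** The strongest reply is that few such patients will appear. Section 1 says NICE does not recommend vismodegib, sonidegib has not been appraised, and the UK has no effective first-line option. The trial is NHS-sponsored, and section 4.4 excludes metastatic disease and Gorlin syndrome. If adding an exclusion would lose few candidates, few pre-treated patients would enter without it. This stands. It makes the top rows of the table the plausible ones and leaves the 20% and 30% rows without support in the document.

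The 31% and 45% are not like for like, and the 45% rests on hedgehog-inhibitor data rather than cemiplimab data. This also stands. The gap between them is not a measured effect of treatment line, so the power figures are illustrative.

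If pre-treated patients respond less often, mixing them in makes a false positive less likely, so the error is on the cautious side. That is true of the test, but it does not settle which population the result describes.

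The title and aim may guide investigators, and section 5 has eligibility confirmed centrally. Both reduce the risk, but neither is a criterion on prior hedgehog-inhibitor use.

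A reader might infer three stronger points that the document does not support:
- *That hedgehog inhibitors are not restricted at all.* Criterion 10 does exclude use within 30 days of the first dose.
- *That the result would be uninterpretable.* Section 6.1 collects cancer history at baseline, so pre-treated patients should be identifiable. The formal test is against a fixed 25%, with no formal comparison against hedgehog inhibitors.
- *That the sample size is wrong.* The stated 37 reproduces.

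**Conclusion.** The mismatch is real. The title, aim and 45% target define a first-line trial, while the eligibility criteria, followed as written, admit patients whom the protocol's own Background calls second line. It should be fixed, but it does not invalidate the design.

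The likely cost in power is small: about 1.2 points for one pre-treated patient in 37 and 2.4 points for two. Losses of 4.7 points (10% share) or 9.9 points (20% share) need about 4 or 7 such patients. These figures rest on an inferred final cut-off of 14 of 37, an assumed share, and a 31% rate used as if it applied at 6 months. The effect on the first-line claim does not depend on those assumptions, although its practical weight grows with the number of pre-treated patients.

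**What to change.** Reconcile sections 4.3 and 4.4 with the title, the aim in section 1 and section 11.1, in one of two ways:

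1. If the question is first-line cemiplimab, make the criteria enforce it by adding an exclusion for any prior systemic hedgehog inhibitor given for BCC.
2. If pre-treated patients are meant to enter, change the first-line label and aim, and revise the 45% assumption and the power that follows from it.

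In either case, identify any pre-treated patients from the baseline cancer history and report the primary response rate with and without them.

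The cost of the first route is one line in an amendment and possibly a few lost candidates, which section 1 suggests would be rare. The second route costs more, because the sample size justification must be redone. The extra reporting uses data already collected.
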